In the proposed serial-dose, parallel design study, we plan to explore the effects of propranolol in combination with early intensive behavioral intervention in children with autism. Propranolol or placebo will be administered at the beginning of behavioral intervention sessions in a double-blinded, counterbalanced manner for the course of twelve weeks. Outcome measures will include assessments of social functioning, language, anxiety, adaptive behaviors, and other autism-related symptoms. This study will allow us to examine the effects of propranolol with multiple doses in a trial setting. In addition, this will be the first exploration of this drug's effects in children with autism, an important area of study given the benefits of early intervention. Previous studies involving pediatric migraine suggest that this drug can be used safely in young children. We will also determine whether measures of autonomic nervous system functioning and anxiety can predict which individuals will respond best to the drug. In this manner, we can begin to optimize and individualize combined treatment approaches for treating core symptoms of autism.

2. Objectives (include all primary and secondary objectives)

We propose to examine the effects of propranolol on social interaction in children with autism undergoing early intensive behavioral intervention (EIBI) in a 12-week, double-blinded, placebo-controlled pilot trial. We will also assess the effects of this combined therapeutic approach on language, anxiety, adaptive behaviors, and other autism-related behaviors in these individuals. Lastly, we will investigate how autonomic nervous system (ANS) activity, as measured by heart rate variability and pupillary light reflex, and baseline anxiety might predict the effects of propranolol on social functioning and our other outcome measures. We hypothesize that concomitant administration of propranolol will enhance the clinical benefit made through EIBI by improving social functioning, language, anxiety, adaptive behaviors, and other autism-related behaviors. We predict that this augmentation of EIBI's effects will only be apparent for the propranolol condition of the study. We also expect that ANS activity and anxiety levels will predict response to propranolol on our outcome measures.

3. Background (briefly describe pre-clinical and clinical data, current experience with procedures, drug or device, and any other relevant information to justify the research)

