During the study, participants will undergo ANS activity and behavioral assessments (discussed below) at three separate study visits at the following time points: (1) prior to drug administration, for establishment of a baseline (week 0); (2) at approximately week 6; and (3) at the end of week 12. Each study visit is expected to last approximately an hour and half.

ANS Measurements: At each study visit, ANS measurements will be performed to assess autonomic activity. Heart rate variability (HRV), measured via electrocardiogram, will be used to assess sympathetic and parasympathetic nervous system activity. Electrodes will be placed on the chest region in the typical manner, and signal from the electrodes will be amplified by an ECG 100C module connected to a BIOPAC MP150 data acquisition system. Measurements will be recorded for a period of 8 minutes, allowing for 3 minutes of acclimation to the equipment.

We will also evaluate ANS activity via the pupillary light reflex (PLR), a simple functional neurological test measuring pupil constriction and recovery in response to stimulation via a short light flash. During the test, the participant will sit comfortably in a

chair or will be seated on a parent's lap about 1 m from the PLR system. A red-filtered movie will be shown on a projector screen behind the PLR system to attract the participant's attention. During the test, participants' PLR will be assessed in both light- and dark-adapted conditions. A total of 10 trials, each lasting 2.5 sec followed by a 25-30 sec interval, will be performed for each stimulation condition.

Behavioral Assessments: Behavioral tasks and questionnaires will also be performed at each study session. The following assessments will be completed by the participant with ASD:

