(2) Interval Medical History Questionnaire: Participants' parents/caregivers will complete a questionnaire about any side effects their child has experienced since the previous study visit, any new medical or psychiatric diagnoses, and any concomitant medications they are taking or have added since the last study visit, and whether they have visited a doctor's office or hospital since their last study visit. This questionnaire is for the purpose of maintaining the safety of participants, as the study staff and PI

will need to ensure that each participant is not experiencing any adverse events throughout the study.

(3) Demographic questionnaire: A questionnaire ascertaining a participant's personal and family demographic information, such as race/ethnicity, handedness, and socioeconomic status, will be completed by the parent/caregiver at the initial study visit only.

(4) Social Responsiveness Scale, second edition (SRS): This 65-item, parent-report measure asks questions about a participants' social awareness, social information processing, capacity for reciprocal social responses, social anxiety or avoidance, and characteristic autistic preoccupations or traits. Depending on the child's age, the preschool or school-age version of the SRS will be administered.

(5) Clinical Global Impression of Change (CGIC) and Clinical Global Impression of Severity (CGIS) scales: To assess overall changes in the participant's ASD-related clinical symptoms, the CGIC and CGIS will be administered. The CGIC consists of a 7-point subjective scale assessing change from baseline. On this scale, scores of 1, 2, and 3 represent marked, moderate, and mild improvement, respectively. A score of 4 represents no change. Scores of 5, 6, and 7 represent mild, moderate, and marked worsening, respectively. CGIC scores from both the parent/caregiver and a blinded clinician will be utilized. The CGIS is a similar 7-point subjective scale for severity.

(6) Autism Impact Measure (AIM): The AIM will be administered to assess the frequency and impact of a participant's ASD-related symptoms. A parent/caregiver is asked a series of 41 questions regarding the frequency and the impact, or interference resulting from, a series of autism-associated behaviors. Overall impact and frequency scores, as well as subscale scores, will be obtained from this measure.

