(7) Vineland Adaptive Behavior Scales-II (VABS): To assess overall adaptive functioning, the VABS will be administered in the form of a structured interview with the parent/caregiver. The VABS is a well validated assessment used for the full range of our subjects' ages and yields standard scores in Communication, Daily Living Skills, Socialization, and Motor Skills. VABS scores for Communication, Daily Living Skills, and Socialization will be monitored in this study.

(8) Aberrant Behavior Checklist (ABC): To assess overall behavioral disturbances, a parent/caregiver of the participants will complete the ABC. This 58-item questionnaire is a well validated, reliable, and widely used assessment tool for interventions for a range of cognitive disorders.

(9) Preschool Anxiety Scale (PAS): To assess anxiety, the PAS will be completed by a parent/caregiver. This 34-item parent-report questionnaire, adapted from the Spence Children's Anxiety Scale (SCAS), yields a total score and five subscale scores based on DSM-IV anxiety disorder structure (separation anxiety, social phobia, obsessive-compulsive disorder, and generalized anxiety), as well as fears related to physical injury.

We will also make efforts to gain the input of participants' parents/caregivers at the outset as well as completion of the study. This will involve the completion of a survey upon study enrollment asking about potential outcomes the parent/caregiver wishes to explore (e.g., gastrointestinal symptoms) in this study. Any suggestions that are not already incorporated to the study and are deemed appropriate and necessary by the PI will

be submitted to the HS IRB as an amendment. Additionally, after completing the study, the participants' parents/caregivers will be asked to complete an exit survey, asking about their child's experience of the study and if they have any suggestions for future studies of a similar nature. This survey will be given to parents/caregivers to complete at the end of the final study visit or mailed when necessary.

We will also make efforts to inform families of the progress of this study via newsletters containing enrollment updates and new (non-study related) findings and news in autism research sent via email on a quarterly basis. Each newsletter will be submitted to the HS IRB for approval prior to being sent out.

b. Study duration and number of study visits required of research participants.

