Propranolol is a beta-adrenergic antagonist that dampens the stress response system. Previous studies from our laboratory indicate a potential effect of propranolol on social and language abilities in adults and adolescents with ASD. This pilot trial investigation will explore the effects of serial doses of propranolol in children with autism who are concurrently undergoing EIBI. We predict that propranolol's effects on stress and anxiety will positively impact social and language abilities in children with ASD and augment the effects of EIBI.

b. Justification and safety information if FDA approved drugs will be administered for non-FDA approved indications or if doses or routes of administration or participant populations are changed.

Propranolol is part of established care for treating pediatric migraine (14, 15, 16) and infantile hemangioma (17, 18), demonstrating its safety for this population. To

minimize risk, the doses to be used for children in the present study were selected as the bodyweight adjusted minimum dose safely used in otherwise healthy adults for test anxiety. The typical doses for test anxiety in adults (10mg) are lower than those for cardiac indications (starting dose for hypertension is 40mg). Participants taking propranolol in this study may be at risk for the side effects described below.

Parents/caregivers and the participants will also be told that there may be other side effects that we cannot predict. Measures to maintain the safety of study participants will be further discussed below. Parents/caregivers of participants will be encouraged to discuss these with the PI ([name]) and/or their own doctor.

- c. Justification and safety information if non-FDA approved drugs without an IND will be administered.

N/A

7. Study Statistics

- a. Primary outcome variable.

We are primarily exploring the effects of propranolol on social abilities, as assessed via the GOSM and the SRS.

- b. Secondary outcome variables.

Our secondary outcome variables include effects on anxiety (assessed via the PAS), language abilities (assessed via the PLS-4), adaptive/global functioning (assessed via the Vineland), and change in clinical impression/impact of ASD symptoms (assessed via CGIC, CGIS, ABC, and AIM).

- c. Statistical plan including sample size justification and interim data analysis.

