To determine the appropriate sample size for this study, we conducted a power analysis based on effect size estimates on our previous study examining the effects of propranolol on social functioning in ASD. The power analysis indicated that a sample size of 20 would achieve a proposed power of 0.80 at the significance level of $\alpha = .05$. Behavioral assessments will be compared across study time points and between drugs (propranolol and placebo) using repeated measures multivariate analyses of variance (MANOVAs). We will use simple linear regressions to determine whether variability in baseline autonomic nervous system functioning or anxiety serve as markers to predict treatment response. Interim data analysis will only be conducted for the purposes of presenting preliminary data at academic conferences. The investigational pharmacy will assist in unblinding collected data for these preliminary analyses, keeping investigators blinded throughout the study.

- d. Early stopping rules.

As this is a pilot trial exploring the effects of propranolol on social and language abilities, there are no behavioral endpoints that we could consider treatment success or failure prior to the completion of the study, thus we would not stop the study based on early evidence of treatment efficacy or futility. If safety becomes a concern due to side effects associated with propranolol, the PI (in consultation with the HS IRB) may decide

to stop the study early. However, this is not expected to occur given the minimal side effects known to be associated with this drug at these doses.

8. Risks

- a. Medical risks, listing all procedures, their major and minor risks and expected frequency.

The medical risks participants may encounter are those associated with taking the drugs used in this study. Below are the descriptions and side effects associated with each drug:

Propranolol [pro-pran'-o-lol] is commonly used to decrease high blood pressure. This drug can cause problems for persons with depression, diabetes, thyroid disease, very slow heart rates, very low blood pressure, fluid in the lungs from heart failure, and asthma. The side effects related to this drug are given below. These symptoms are most present within 5 hours of the drug administration. None of these symptoms will be present once the single dose is washed out of the system, which can take up to 24 hours.

- Very Likely: Decreased Blood Pressure and/or Slow Heart Rate

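### Baseline PAS is to be tested as a marker for the PAS outcome by one-predictor regression, which often gives a significant slope with no drug effect and cannot show response to propranolol

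*Combined protocol and SAP*

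**What the plan says.** Section 2 (Objectives) proposes to examine how autonomic activity and "baseline anxiety might predict the effects of propranolol on social functioning and our other outcome measures". It adds the expectation that anxiety levels will predict response to propranolol. The Abstract gives the purpose: to find which children respond best to the drug, so that combined treatment can be individualised.

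Section 7b lists among the secondary outcomes "effects on anxiety (assessed via the PAS", so anxiety is one of the outcomes to be predicted. Section 4a, Behavioral Assessments, item (9), names the instrument: "To assess anxiety, the PAS will be completed by a parent/caregiver". No other dedicated anxiety scale appears. On timing, section 4a says "Behavioral tasks and questionnaires will also be performed at each study session", which means week 0, about week 6 and the end of week 12.

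For the marker analysis, section 7c plans "simple linear regressions to determine whether variability in baseline autonomic nervous system functioning or anxiety serve as markers to predict treatment response". It does not say whether response is a change score or a week-12 score, or whether one arm or both enter the regression. It gives no treatment-by-marker term. The placebo arm is mentioned for the repeated measures MANOVAs but not for the marker regressions.

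**The concern.** Read together, these sections put the week-0 PAS on the right-hand side of a regression whose left-hand side is the PAS outcome. That baseline anxiety means the week-0 PAS is an inference, but the documents name no other candidate.

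A scale regressed on its own earlier value has a non-zero slope in any group of children, treated or not. If response is change from week 0, children with high starting scores tend to fall back and the slope is negative. If response is the week-12 score, children who start high tend to stay high and the slope is positive. A test of zero slope therefore does not test whether anxiety marks response to propranolol.

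The change-score version matters most, because the artefact points the way the plan expects: the most anxious children would appear to improve most. A reader could take that as support for selecting anxious children for the drug.

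**Working it through.** **Plan's own figure.** The plan states none for the marker analysis. The sample size of 20 for power 0.80 in section 7c concerns the drug effect on social functioning; it comes without an effect size and does not bear on this point.

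**Inputs from the documents.** 30 children (section 4a), half to each arm, so 15 on propranolol; significance level 0.05 (section 7c).

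**Assumptions.** The test is two-sided, since the plan does not state sidedness. PAS scores are bivariate normal with equal variance at week 0 and week 12. Their correlation r (stability) is not given, so a range is shown. There is no drug effect.

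**Change score.** Let X be the week-0 score, Y the week-12 score and s² their common variance.
- Cov(Y − X, X) = rs² − s² = −(1 − r)s²
- Var(Y − X) = 2(1 − r)s²
- corr(Y − X, X) = −(1 − r)/√(2(1 − r)) = −√((1 − r)/2)

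For r = 0.6 this is −√0.20 = −0.447. For r = 0.8 it is −√0.10 = −0.316.

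Putting the correlation c into t = c√(n − 2)/√(1 − c²):
- r = 0.6, n = 30: −0.447 × 5.292/0.894 = −2.65 (critical value 2.05)
- r = 0.8, n = 30: −0.316 × 5.292/0.949 = −1.76 (critical value 2.05)
- r = 0.6, n = 15: −0.447 × 3.606/0.894 = −1.80 (critical value 2.16)
- r = 0.8, n = 15: −0.316 × 3.606/0.949 = −1.20 (critical value 2.16)

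So the expected t lies close to, or beyond, the critical value when nothing is happening.

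**Simulated chance of p < 0.05 with no drug effect** (200,000 trials per cell; nominal 5%):

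| Stability r | Change, n = 15 | Change, n = 30 | Week-12 score, n = 15 | Week-12 score, n = 30 |
|---|---|---|---|---|
| 0.6 | 40% | 72% | 70% | 96% |
| 0.7 | 30% | 58% | 88% | over 99% |
| 0.8 | 21% | 41% | 98% | 100% |
| 0.9 | 12.5% | 22% | 100% | 100% |

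Here n = 15 is the propranolol arm alone and n = 30 is both arms pooled. The change columns show regression to the mean. The week-12 columns show tracking, a different phenomenon with a positive slope.

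**Interaction test.** Compare the PAS slope on baseline between arms. In each arm the slope for change equals the slope for the week-12 score minus 1, so the difference between arms is the same under either definition of response. With no drug effect the slopes are equal and the coupling cancels. Simulated false-positive rates with both arms (n = 30) were 4.8% to 5.0% for every r from 0.3 to 0.95.

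**Power of that test.** It is limited. With 15 per arm, a slope difference of 0.5 residual standard deviations per baseline standard deviation is detected in 23% of simulated trials. A difference of 1.2 is needed for 81%.

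**The case against.** Several points stand. The inflation is not a certainty: in the propranolol arm alone, the natural sample for response to propranolol, the change-score slope misses significance more often than not at stability 0.6 or above. If the PAS were very stable the excess would shrink; at r = 0.9 the rate is 12.5% with 15 children. The documents give no stability figure. The pair concerned is one marker and one secondary outcome in a pilot trial, and the MANOVA comparison of the arms is untouched.

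It can also be said that response is undefined, so the fault depends on how the gap is filled. That does not help, because both natural definitions fail, though in different ways. Only the change-score version would suggest that anxious children gain most.

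A reader might go further and infer that the marker analysis of the primary Social Responsiveness Scale (SRS) is biased too. Section 4a says the SRS covers "social anxiety or avoidance", the PAS has a social phobia subscale, and both are parent or caregiver reports. The documents do not support that as a finding. If the scales have stable true scores and independent errors, regressing SRS change on baseline PAS keeps its 5% rate. Inflation needs correlated same-visit errors, or baseline PAS relating to later SRS only through the observed baseline SRS. Nothing in the documents settles which applies.

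**Conclusion.** The concern holds for the PAS outcome regressed on baseline PAS. Followed as written, the plan tests a slope that is non-zero without any drug effect. With PAS change, the false-positive rate is about 21% to 40% with 15 children and 41% to 72% with 30, for assumed stability 0.8 down to 0.6. With the week-12 score it is 70% to 98% and 96% to 100% as stability rises from 0.6 to 0.8. These figures rest on the assumed stability, equal variances, normality and a two-sided test.

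The plan does not guarantee a spurious marker; it makes one much more likely than the nominal 5%. No size of bias can be claimed for the SRS or the other outcomes. For those, the remaining weakness is that a regression without a placebo contrast cannot separate a marker of general course from a marker of response to the drug.

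**What to change.** In sections 2 and 7c:

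1. State that a one-predictor regression of the PAS outcome on baseline PAS will not be interpreted as evidence of a marker of drug response.
2. Either drop that pair, or test it with a model containing arm, baseline PAS and their interaction, fitted to both arms. Preferably use the same form for every marker and outcome, since the question is who responds to propranolol and a concurrent placebo arm already exists.
3. Define response for each outcome.
4. Label the marker results exploratory.

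Do not offer the outcome's own week-0 score as a covariate as the sole cure. Whether it removes or creates bias depends on measurement error that the documents do not quantify.

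The cost is plan wording and two further degrees of freedom per regression (arm and interaction). Power for interactions is low with 30 children, so a null result will be uninformative. No new data are needed.
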